## 2. Introduction of a third phase of the study

At the time of the start of the Papillon study (June 2018), there was no experience nor publication of vaccination with Gardasil9 in women living with HIV (WLHIV). We have then started our study by a first open label part including 45 patients to observe if tolerance and safety was equal to what was described in HIV-negative women. At the end of this open label part (from June 2018 to January 2019), our data on safety were reassuring and we proceeded to the randomized phase as described upper (from January 2019 to February 2021).

Because of the SARS-CoV2 pandemic, the enrollment had been slowed down and by February 2021, we had randomized 102 WLHIV instead of 150.

As we needed to end the study enrolment by September 2019 because of budget constraints, we have introduced an amendment to give two doses (as in ARM A) to all the patients enrolled from February 25th 2021.

We plan to analyze the results in intention-to-treat on the randomized cohort (n=102), and in On-treatment on the whole cohort (n=169).

## 3. Extension of the study follow-up

In order to assess long term persistence of antibody response, we will collect serum samples at different time points after completion of the vaccine schedule (24, 36, 48 and 60 months.). If the time point is exceeded, plasma samples collected during

routine care will be retrieved for the AIDS reference laboratory (VUB-LHUB ULB). Signature of a new informed consent will be required before collecting stored or new samples.

### **Inclusion criteria**

- HIV-positive woman
- Age 15-40 years
- Undetectable HIV viral load (HIVRNA <400 cp/ml) for at least 6 months (i.e: having at least two separate VL<400 cp/ml at 6 months intervals; the most recent VL<400 cp/ml may be the screening CV for the study).
- No planned pregnancy foreseen for the next 7 months and use of contraception such as condom, hormonal contraception or intrauterine device
- IC signed

### **Exclusion criteria**

- Previous hysterectomy or conisation
- Previous or current biopsy-proven cervical, vulvar or vaginal HPV-associated lesion defined as  $\geq$ CIN2, VIN2, VaIN2 or invasive carcinoma
- Previous vaccination against HPV (at least one dose)
- Ongoing or planned pregnancy foreseen in the next 7 months
- Other immunodeficiency conditions such as ongoing or previous (within 6 months) chemotherapy against cancer or chronic systemic corticosteroids treatment or immunosuppressive therapy after transplantation
- Any condition contraindicating intramuscular injection such as warfarin therapy.

### **Site of enrolment and study**

AIDS reference center in Saint-Pierre University hospital

### **Ethical committee**

Saint-Pierre University hospital

### **Informed consent**

All patients have to read and sign the inform(s) consent(s) before entering the study.

For participants aged 18 years or more, there is one IC to be read and signed before entering the main study.

For participants aged less than 18 years old, there are two separated forms: one for the participant and one for her parents or legal representatives; these two forms have to be signed before entering the study.

For persons participating to the sub-study on cellular immune response to the vaccine (they will be aged 18-40), there will be another separated IC to be signed.

## Flowchart

### To be performed at baseline:

- Informed consent(s) signature
- Measure of serum antibodies against HPV 6/11/16/18/31/33/45/52/58 (1 10 ml tube) by 9cLIA by Merck USA.
- Measure of lymphocytes T CD4+ level and HIV viremia if there is no previous sample up to 6 months before baseline.
- Cervical smear on a liquid based samples (Cytoprep) taken by the gynecologist for cytology and HPV detection (to be performed by the national reference centre for HPV, AML, Antwerpen) if there is no previous sample up to 6-12 months before baseline. These samples will not be taken if the participant has never experienced vaginal sexual intercourse.
- ONLY FOR THE CELLULAR IMMUNE RESPONSE SUBSTUDY: an additional specific IC should be signed and a sample of 50-100 ml should be taken.
- Randomisation (after December 2018 amendment): patients will be allocated to one of the two arms by random randomization through a software program. The result of the allocation will be known to the patient, to his healthcare providers and to the study team.
  - ARM A: vaccination at time 0 and 6 and a later booster if **needed**
  - ARM B: vaccination at time 0, 2 and 6 months
  - **Vaccine administration after randomisation**

Gardasil9 (Merck®) first dose will be administrated intramuscularly in the deltoid while the patient is lying down. The patient will remain lying 15 minutes after the injection.

### First safety assessment after vaccination

The patient will be contacted by phone by the research team scheduled at least 48 hours and maximum 7 days after vaccine dose to evaluate the safety and tolerance of the vaccine with a questionnaire on local reaction (size, redness, pain and swelling), systemic reaction (fever, malaise and fatigue) or any other side effect. In case of any usual complain > grade mild, or the presence of an unusual complain, the patient will be assessed by a visit and physical examination performed by the research team.

## **Month 2 (only for patients in ARM B)**

Gardasil9 second dose will be administrated intramuscularly in the deltoid while the patient is lying down. The patient will remain lying 15 minutes after the injection.

## **Second safety assessment after vaccination**

The patient will be contacted by phone by the research team scheduled at least 48 hours and maximum 7 days after vaccine dose to evaluate the safety and tolerance of the vaccine with a questionnaire on local reaction (size, redness, pain and swelling), systemic reaction (fever, malaise and fatigue) or any other side effect. In case of any usual complain > grade mild, or the presence of an unusual complain, the patient will be assessed by a visit and physical examination performed by the research team.

## **Month 6**

Gardasil9 second (ARM A) or third (ARM B) dose will be administered intramuscularly in the deltoid while the patient is lying down. The patient will remain lying 15 minutes after the injection.

## **Second (ARM A) or third (ARM B) safety assessment after vaccination**

The patient will be contacted by phone by the research team scheduled at least 48 hours and maximum 7 days after vaccine dose to evaluate the safety and tolerance of the vaccine with a questionnaire on local reaction (size, redness, pain and swelling), systemic reaction (fever, malaise and fatigue) or any other side effect. In case of any usual complain > mild, or the presence of an unusual complain, the patient will be assessed by a visit and physical examination performed by the research team.

## **Month 7**

Measure of lymphocytes T CD4+ level and HIV viremia.

Measure of serum antibodies against HPV 6/11/16/18/31/33/45/52/58 (1 10 ml tube)

ONLY FOR THE CELLULAR IMMUNE RESPONSE SUBSTUDY: a sample of 50-100 ml will be taken.

## **Month 18-24**

- Measure of serum antibodies against HPV 6/11/16/18/31/33/45/52/58 (1 10 ml tube) by IgG LIA by Merck USA.
- Cervical smear on a liquid based samples (Cytoprep) taken by the gynecologist for cytology and HPV detection. These samples will not be taken if the participant has never experienced vaginal sexual intercourse.

## **Procedures for Collection and Handling of Study Specimens:**

### **1/Measure of serum antibodies against HPV 6/11/16/18/31/33/45/52/58 (one 10 ml tube)**

For each visit that requires a serum specimen for anti-HPV measurements, a 10 mL (nonheparinized, non-serum separator, red-top tube) blood specimen will be collected and will be separated to avoid hemolysis. A minimum of 3 mL of serum will be aliquoted to a vial. An additional 1.5 mL of serum (Retention Serum) will be aliquoted to a vial.

After the serum has been processed, the vials will be transferred to the freezer (-20°C or lower) without delay. All serum samples will be kept in the freezer until they are shipped on dry ice; the transport tube will be a 2ml cryovials.

Centrifuging will be done per protocol with sera frozen.

"Serum" vials will be stored at the site at -20°C (or lower) until shipped on dry ice to the lab. The freezer used to store the vials must be a non-frost-free freezer. All available serum will be used for conducting assays specified in the clinical protocol. Serum may also be used during the clinical trial, for further HPV immunologic testing in addition to tests specified in the protocol.

Retention Serum vials will remain stored at the site at -20°C (or lower). The freezer used to store the vials must be a non-frost-free freezer. The site will ship "Retention Serum" separately from the "Serum" sample.

The rest of the sample will be kept on site frozen as a backup sample.

### **Booster dose in ARM A**

A third booster dose of Gardasil9 will be given in women from ARM A if they fail to develop antibodies against any of the HPV genotypes contained in the vaccine. As the analysis of the antibodies will be performed in MERCK laboratory in the USA in batches, the booster dose will be given as soon as the results of the antibodies measurement will be known which is predicted to be as soon as possible just after Month 7 of the last enrolled patient.

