**Etude Papillon**

Phase IV prospective study evaluating the reactogenicity and immunogenicity (both humoral and cellular responses) and the safety of the 9valent vaccine against HPV (Gardasil9®Merck) in HIV-positive women aged 15-40 years with fully suppressed HIV viremia on combined antiretroviral therapy. After a first open phase evaluating tolerability of Gardasil9, women will be randomized between two different doses schedules: in the first schedule, women will receive 2 doses at time 0 and 6 months and a third dose between 18-48 months if their antibody levels are insufficient; the second schedule will be 3 doses at 0, 2 and 6 months. Primary outcome is the non-inferiority of the rate of seroconversion against each HPV vaccine genotypes in women seronegative at baseline after either 2 or 3 doses of vaccination (month 7). Secondary outcomes are rate of seroconversion after 3 doses if they have received a third dose, completion of vaccine schedule, vaccine safety, antibody titles, and induction of cellular immunity against HPV contained in the vaccine, incidence of cervical HPV infection and incidence of abnormal cytology after vaccination.

Date: 15/12/2023

Author: [name] and [name] [name]

Version: 7

NCT NCT03391921

EUDRACT 2018-000228-33

FAMHP: FADG/R&D/BEN/mmn

Centre de Référence SIDA

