## **Number of patients**

Study: 200 patients

First phase: open label: 3 doses of vaccine at 0, 2 and 6 months

Second phase (150 patients): randomized study comparing two arms:

- ARM A schedule of vaccination (75 patients): 0 and 6 months and a facultative later booster dose if antibodies level insufficient at month 7
- ARM B schedule of vaccination(75 patients): 0,2 and 6 months

Substudy on cellular immune responses in a subset of patients: 40 patients and separated informed consent

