**After completion of the vaccine administration (2 or 3 doses).**

**Women included will be contacted in order to collect a serum sample and will sign a new informed consent. If the time point is exceeded, we will retrieved plasma samples collected during routine care for HIV viral load determination (stored at the AIDS Reference Laboratory-LHUB ULB).**

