**Secondary outcomes**

- Completion of vaccine schedule.
- Safety and clinical tolerance of the vaccine administration.
- Impact on T-lymphocytes CD4+ counts and HIV viremia at month 7.
- Rate of seroconversion of neutralizing antibodies against each HPV vaccine genotypes namely 6/11/16/18/31/33/45/52/58 among women seronegative at baseline for HPV vaccine genotypes, by measuring neutralizing antibody against the 9 vaccine genotypes of HPV at Month 18, **24, 36, 48 and 60** compared to baseline.
- Measure of neutralizing antibodies title against each HPV vaccine types at baseline, month 7 and 18
- Assessment of long term persistence of HPV-specific antibody responses at 24,36,48 and 60 months after completion of the last vaccine administration dose.
- The cellular immune response against HPV 16/18/31/52/58 will be assessed in a subgroup of patients (n=40, 20 in each arm) on PBMC samples tested. For this analysis, a separated IC should be first signed by the patient.
- Incidence and prevalence of HPV infections and of abnormal cervical cytology performed by cytology and PCR on cervical swab at baseline and 12 months after the end of vaccination.

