Antibodies title peaks one month after last vaccine dose than decrease to a plateau and stabilize around month 12 after receiving the last dose. In this study, antibodies against HPV will be measured at baseline, month 7 (that is to say 1 month after receiving 2 or 3 doses depending in which arm the patient has been randomized to) and month 18 (or 12 months after receiving the second or third dose, reflecting the stabilized antibodies level. We expect that two doses of vaccine in HIV-positive patients with well controlled HIV viremia under cART for at least 6 months could induce seroconversion in at least 80% of the patients seronegative at baseline whereas the seroconversion rate is expected to be 95% after 3 doses according to previous studies using the quadrivalent vaccine in HIV-positive patients. We find a minimum of 80% efficacy in the two doses arm acceptable as in this arm the vaccine costs would decrease by 33%, administration will be easier, the risk of local reaction after injection could also be decreased and compliance with the whole vaccine administration could be improved.

Regarding the number of patients that should be enrolled in the study, we considered a sample size calculation based on the SAS 9.4 program for comparing two independent proportions (1:1 allocation in a non-inferiority trial) by a Pearson Chi-square test. If we consider 95% rate of seroconversion for ARM B (3 doses vaccines) and 80% for ARM A (2 doses vaccines) with a significance level test of 0.05 (alpha) and an 80% statistical power (Beta), we found that 60 patients per

arm would be needed (120 patients in total). We would then need in total 150 women to be randomized taking into account the possibility of follow-up lost.

The purpose of vaccinating women is to induce antibody response against each HPV genotype contained in the vaccine and in particular against the 7 high-risk genotypes that induces cancer. If, after 2 doses of vaccine (ARM A), the month 7 antibodies measure shows absence of seroconversion against one of the HPV genotypes contained in the vaccine, the participant will receive a third booster dose of Gardasil9.

In order to assess long term persistence of HPV-specific antibody responses, the follow up will be prolonged to the following time points after completion of the vaccine administration : 24, 36, 48 and 60 months.

The role of basal immune activation on seroconversion rate and long term persistence of antibody responses, will be assessed.

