#### 5/Completion of the vaccine schedule

Comparison of the proportion of women achieving full course of vaccine administration in each arm, namely for ARM A receiving 2 doses and for ARM B receiving 3 doses.

6/ Proportion of patients needing a booster dose (*i.e.*..a third dose) in ARM A  
If after 2 doses of vaccine (ARM A), the month 7 antibodies analysis shows absence of seroconversion against one of the HPV genotypes contained in the vaccine, the participant will receive a third booster dose.

7/ Impact of basal immune activation (levels of CD25, sCD14, IP-10, IL-6, TNF- $\alpha$ , d-Dimers, CRP) on the seroconversion rate and long term antibody persistiance

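### ARM A's late antibody results mix samples taken before and after a booster triggered by the month-7 result, so they cannot be read as two-dose durability

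*Protocol*

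**What the plan says.** **Who gets the third dose.** The Protocol's Number of patients section defines ARM A as "0 and 6 months and a facultative later booster dose if antibodies level insufficient at month 7". Design of the study sets the trigger as the case where "the month 7 antibodies measure shows absence of seroconversion against one of the HPV genotypes contained in the vaccine". Item 6 under Completion of the vaccine schedule repeats it, and Booster dose in ARM A states: "A third booster dose of Gardasil9 will be given in women from ARM A if they fail to develop antibodies against any of the HPV" (vaccine types). No further dose is described for an ARM B woman who fails on a genotype.

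**When it is given.** The cover page describes "a third dose between 18-48 months if their antibody levels are insufficient". Booster dose in ARM A instead ties it to the arrival of batched laboratory results, "predicted to be as soon as possible just after Month 7 of the last enrolled patient".

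**What is measured late.** Secondary outcomes in the Executive summary has three relevant items:
- "Rate of seroconversion of neutralizing antibodies against each HPV vaccine genotypes namely 6/11/16/18/31/33/45/52/58 among women seronegative at baseline", at months 18, 24, 36, 48 and 60 compared to baseline;
- antibody titres at baseline, month 7 and month 18;
- persistence at 24, 36, 48 and 60 months, counted from the last dose given.

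The December 2023 amendment likewise places the added time points "After completion of the vaccine administration (2 or 3 doses").

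**Where the booster does appear as an outcome.** The cover page lists seroconversion after three doses among women given a third dose. Item 6 reports the proportion of ARM A needing one. The first of these is not carried into the detailed outcome lists.

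**The concern.** The booster is given in one arm only, and the women who get it are those with a failure on the outcome being studied. One missed genotype leads to a dose containing all nine. From then on ARM A's failures have had another chance to convert, and boosted women's antibodies to genotypes they had already responded to may rise as well. ARM B keeps its failures.

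The Rationale asks whether two doses are not inferior to three in women with HIV. A late ARM A figure that pools two-dose women with boosted women does not answer that question for the longer term, although it could be taken as an answer. Counting persistence from the last dose adds to the problem: on its plain wording, a boosted woman starts again at time zero and is then tabulated beside women whose last dose was at month 6.

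Leaving boosted women out would not solve it. Among women seronegative at baseline for all nine types, those not boosted are by the trigger rule the ones who converted on every type. Without the boosted women, ARM A would start from 100% at month 7 by construction.

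**Working it through.** **Inputs.** Month-7 seroconversion of 80% in ARM A and 95% in ARM B, alpha 0.05 and power 80% come from Design of the study. The share r of month-7 non-responders who convert after the booster is not in the protocol and is varied here. So is w, the share of converters still seropositive at the late visit.

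**1. The plan's own figure.** For a pooled chi-square comparison, n per arm = [z(α)·√(2·p̄·q̄) + z(power)·√(pA·qA + pB·qB)]² / d², with p̄ = 0.875 and d = 0.15. One-sided 0.05 gives [1.645 × 0.4677 + 0.842 × 0.4555]² / 0.0225 ≈ 59.1, so 60 per arm, as stated (two-sided gives 76). The 80% and 95% are therefore the plan's working rates per genotype.

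**2. Late rate in ARM A, no waning.** Late ARM A = 0.80 + 0.20·r, against 0.95 in ARM B and 0.80 for two doses alone.

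| r (assumed) | Late ARM A | Late ARM B |
|---|---|---|
| 0.50 | 90% | 95% |
| 0.75 | 95% | 95% |
| 0.95 | 99% | 95% |

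Break-even: r = (0.95 − 0.80)/0.20 = 0.75.

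**3. With waning.** If all converters keep the same w, it cancels and break-even stays at 0.75. If boosted women have not yet waned and the others have, 0.80·w + 0.20·r = 0.95·w gives r = 0.75·w: 0.675 at w = 0.90 and 0.60 at w = 0.80.

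**4. How many women are boosted.** Take a woman seronegative at baseline for all nine types, with 80% conversion per type. If failures overlap completely, 1 − 0.80 = 20% are boosted; if they are independent, 1 − 0.80⁹ = 87%. Under independence, 1 − 0.80⁸ = 83% of responders to a given type would be boosted because of another type. In ARM B the share failing at least one type is 5% to 1 − 0.95⁹ = 37%, with no further dose.

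**5. Which visits are affected.** Randomization ran from January 2019 to February 2021, and enrolment continued from 25 February 2021. The stated enrolment end of September 2019 cannot be right, so assume the last enrolment fell between February and September 2021. Adding seven months, the booster under the Booster dose in ARM A section comes no earlier than September 2021 to April 2022.

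| Enrolled | Earliest study month of booster |
|---|---|
| January 2019 | 32–39 |
| January 2020 | 20–27 |
| February 2021 | 7–14 |

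Going back 18 months, a month-18 sample taken on time precedes the booster for women enrolled before about March to October 2020, and can follow it for later enrollees.

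**6. The clock.** For an unboosted ARM A woman, 24 months after the last dose is study month 6 + 24 = 30. For a January 2019 enrollee boosted at month 32–39, it is study month 56–63, after a fresh third dose. Both would be entered as 24-month persistence.

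**The case against.** - **This is detail for the statistical analysis plan.** That plan is not at hand and may hold a rule. But the protocol's own definitions produce the mixing: all baseline-seronegative women are compared with baseline, and persistence time runs from the last dose. The wording about two or three doses might mean only the two initial schedules. The clock would then not restart, but samples before and after the booster would still be pooled.
- **ARM A is the boosted strategy.** This stands. Several sections define the arm with the conditional third dose, so late results by randomized arm validly estimate that strategy. The error would lie in reading them as a two-dose effect.
- **The booster is not ignored.** This also stands. A reader might infer that the plan takes no account of it, but the cover page has a third-dose outcome and item 6 counts the women boosted.
- **No late comparison between arms is specified.** Correct: late seroconversion is set against baseline. The break-even describes side-by-side rates, not a planned test.
- **The magnitude is an extreme case.** The protocol presents 80% as a minimum, the 87% needs independent genotypes, and r is assumed. The arithmetic shows that the deficit could disappear, not that it will.
- **Titres.** A reader might infer that all late titres are affected. They are planned only to month 18, which precedes the booster for earlier enrollees.
- **Purpose of the extension.** A reader might suppose that follow-up was extended to test two-dose durability. The December 2023 amendment names basal immune activation and long-term persistence instead.

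**Conclusion.** The point holds in a limited form. ARM A's 24 to 60 month results, and month 18 for later enrollees, estimate two doses plus a booster where needed and cannot support a statement about how long two doses last. At the plan's 80% and 95%, without waning, a 15-point month-7 deficit disappears if 75% of non-responders convert after the booster, or 60% to 67.5% if only the unboosted have waned to 80% to 90% still seropositive. These break-evens rest on assumed r and w. Between 20% and 87% of ARM A could be boosted, depending on how far failures overlap across genotypes.

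The documents do not support going further. The month-7 primary outcome precedes any booster and is not touched. The as-randomized late result is valid for the strategy it describes. Nothing shows that ARM A will overtake ARM B, only that it could while two doses alone were worse. The change should be made before the late results are analysed, but the flaw does not invalidate the trial.

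**What to change.** 1. Record the booster date against every serum or plasma sample.
2. Report late results by randomized arm in two labelled forms:
   - (a) *As randomized, booster included*: all women, with time counted from a common origin in both arms, for example the month-6 dose.
   - (b) *Two-dose durability*: a genotype failed at month 7 counts as non-seroconverted from then on; a boosted woman's other genotypes use only samples taken before the booster.
3. Attach a sensitivity analysis to (b), for example bounds with the censored results taken as all seropositive and then all seronegative. Censoring at the booster depends on month-7 response and probably removes weaker responders. Stored routine plasma may fill some gaps, but it is allowed only where a time point has been exceeded and with new consent, so matching pre-booster samples are not assured.
4. Draw no conclusion on two-dose persistence from (a).
5. Carry the cover page's third-dose outcome into the detailed outcome lists, and state how boosted ARM A women are classed in the On-treatment analysis (n=169).
6. Reconcile the booster timing on the cover page with that in Booster dose in ARM A, and the time origins of the late outcomes with each other.

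The cost is protocol and analysis wording plus one date per boosted woman linked to her samples, with no new visits. The downside is fewer usable ARM A samples at the latest time points in (b).
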